2.6 Efficacy evaluation

All efficacy analyses will be performed on the FAS and selected analyses will be repeated on the PPS. Measurements made after patients discontinue randomized treatment (off-treatment measures) will not be used for any efficacy evaluation.

2.6.1 Analysis of the primary and key secondary variables

The primary objective is to demonstrate the superiority of either QMF149 150/160 µg to MF 400 µg or QMF149 150/320 µg to MF 800 µg in terms of trough FEV₁ after 26 weeks of treatment. The key secondary objective is to demonstrate the superiority of QMF149 (150/160 µg and 150/320 µg combined) to MF (400 and 800 µg combined) in terms of ACQ-7 after 26 weeks of treatment.

2.6.1.1 Variables

2.6.1.1.1 Primary variable trough FEV₁

Trough FEV₁ is defined as the average of the two FEV₁ measurements taken 23 hr 15 min and 23 hr 45 min post-evening dose. Trough measurements will be done at Day 2, Day 184 (Week 26, the primary endpoint) and Day 365.

If any of the 23 hr 15 min and 23 hr 45 min values contributing to the trough FEV₁ are collected within 3 months of a single depot corticosteroid injection, or within 7 days of systemic corticosteroid use, or within 6 hours of rescue medication, or if actual measurement times are outside of the 22 - 25 hour post-evening dose time window for o.d. regimens (or 8 – 13 hour post-morning dose time window for b.i.d. regimens), then the individual FEV₁ value will be set to missing. If one of the two values is missing (or set to missing) then the remaining non-missing value will be taken as trough FEV₁. If both values are missing, then trough FEV₁ will be missing.

2.6.1.1.2 Key secondary variable ACQ-7 score

The ACQ-7 measures asthma symptom control and consists of 7 items: 5 on symptom assessment, 1 on rescue bronchodilator use, and 1 on airway calibre (FEV₁ % predicted). Patient recall is considered 1 week. All 7 questions of the ACQ-7 are equally weighted. Items 1-5 are scored along a 7-point response scale, where 0 = good controlled and 6 = poorly controlled. Item 6 is scored between 0 = no rescue medication and 6 = More than 16 puffs/inhalations most days. The 7th item will be scored by the investigator based on the FEV₁ % predicted from the masterscope at the site (i.e., Score = 0 means > 95% of predicted FEV₁, 1 = 90 – 95%, 2 = 80 – 89%, 3 = 70 – 79%, 4 = 60 – 69%, 5 = 50 – 59%, and Score = 6 means < 50% of predicted FEV₁). The total score is calculated as the mean of all questions. The mean will be calculated as the sum of scores divided by the number of questions that were answered, as long as there were at least 6 questions answered and the missing question is neither Question 1 ('On the average, during the past week, how often were you woken by your asthma during the night?') nor Question 7. In case of one missing response (not Question 1 or Question 7), that missing

response will be imputed as per the method given in the following paragraph and then the ACQ score will be calculated.

For a missing individual item while on-treatment, the interpolation method using either previous or subsequent completions of the questionnaire (ACQ User Guide, 2004) will be used. For instance,

Item	Visit 1	Visit 2
1	4	6
2	3	5
3	0	0
4	4	4
5	0	0
6	2	Missing
7	5	6

Total Visit 1 score for items answered on both visits is $4+3+0+4+0+5 = 16$ (A).

Total Visit 2 score for items answered on both visits is $6+5+0+4+0+6 = 21$ (B).

Item 6 score at Visit 1 = 2.

Item 6 score at Visit 2 = $B/A * 2 = 21/16*2 = 2.63$.

The ACQ score for Visit 1 is $(4+3+0+4+0+2+5)/7 = 2.57$

The ACQ score for Visit 2 is $(6+5+0+4+0+2.63+6)/7 = 3.38$

For baseline, missing item at Day 1 will be imputed by using Day -14 data or data from any unscheduled run-in visit, whichever is later. For post-baseline visits, missing items will be imputed by using data from subsequent visit first, if these are not available, data from previous visit will be used for imputation of the missing item. To clarify, for imputation of the first post-baseline value, if the second post-baseline assessment is not available, the value of the baseline assessment will be used. If there are two assessments from the same day, the first will be used only and the second ignored even for imputation.

ACQ-7 measurements are scheduled for Days -14, 1, 30, 86, 183, and 364.

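### The ACQ-7 missing-item rule gives two scores for the same case and sets no limits on the imputed item: wrong as written, but minor.

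*SAP*

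**What the plan says.** SAP 2.6.1.1.2 fixes the item ranges: "Items 1-5 are scored along a 7-point response scale, where 0 = good controlled and 6 = poorly controlled". The rescue-use question has the same limits: "Item 6 is scored between 0 = no rescue medication and 6 = More than 16 puffs/inhalations most days". Item 7 is also scored 0 to 6.

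For one missing item among questions 2 to 6 it gives two instructions.

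- The first is a mean of what was answered: "The mean will be calculated as the sum of scores divided by the number of questions that were answered". A condition is attached, "as long as there were at least 6 questions answered and the missing question is neither Question 1", and Question 7 is barred in the same way. With one item missing, the divisor is 6.
- The next sentence has the condition "In case of one missing response (not Question 1 or Question 7", which is the same case. It says that the missing "response will be imputed as per the method given in the following paragraph and then the ACQ score will be calculated". The example that follows divides by 7.

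The method is described as follows: "For a missing individual item while on-treatment, the interpolation method using either previous or subsequent completions of the questionnaire". The example multiplies the reference-visit item by B/A. Here A and B are the sums, at the reference and the current visit, of the items answered at both.

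On the choice of reference after baseline, "missing items will be imputed by using data from subsequent visit first", with the previous visit as second choice. A missing Day 1 item takes its reference from Day -14 or a later unscheduled run-in visit.

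The section sets no limit on the imputed value and no rule for A = 0. Protocol 6.4.2.1 says only that the score is the mean of seven items. SAP 2.6.2.8 sends missing AQLQ items through a similar method.

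**The concern.** ACQ-7 at Week 26 is the only key secondary endpoint and belongs to the family with type I error control (SAP 2.6.1.3). Its derivation should give each patient one valid value, fixed before unblinding. As written it may not:

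- two programmers could defend different scores for the same form;
- an imputed item can lie outside the scale;
- the formula can divide by zero;
- the score can depend on the date of the data cut.

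The SAP guards against implausible values elsewhere. It excludes FEV1 above 7 L (2.6.2.2) and sets more than 30 puffs in 12 hours to missing (16.1.9.3.2). It has no such check on a value that its own formula produces.

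**Working it through.** **Inputs.** Item ranges, both scoring instructions, the worked example and the choice of reference visit: SAP 2.6.1.1.2. Entry criterion ACQ-7 ≥ 1.5 at Visits 101 and 102: protocol 4.1. Planned difference 0.15, 400 patients per arm, 10% dropout: SAP 2.10. The documents give no rate of missing items.

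**Formulas.** Imputed item = (B/A) × reference item. Interpolated score = (B + imputed item)/7. Mean-of-answered score = B/6.

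**1. The SAP's example.** A = 16, B = 21, reference item 2.
- Imputed item: 21/16 × 2 = 2.625 (SAP: 2.63).
- Interpolated score: (21 + 2.625)/7 = 3.375 (SAP: 3.38), so the figure is reproduced.
- Mean of answered: 21/6 = 3.50.
- Difference: 0.125.

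**2. Values above 6.** The imputed item exceeds 6 whenever B/A is greater than 6 divided by the reference item: above 2 for a reference item of 3, above 1.5 for 4, above 1 for 6. With reference items 1, 1, 1, 1, 1, 3, 1, item 6 missing now and B = 20:

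| Quantity | Calculation | Result |
|---|---|---|
| Imputed item | 20/6 × 3 | 10 |
| ACQ-7 as written | 30/7 | 4.29 |
| ACQ-7 with item limited to 6 | 26/7 | 3.71 |
| Mean of answered | 20/6 | 3.33 |

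The gap between the first and last scores is 30/7 − 20/6 = 0.95. Of this, 4/7 = 0.57 comes from exceeding the scale. The other 0.38 is an ordinary difference between two methods.

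**3. A = 0.** An eligible patient has a run-in and baseline ACQ-7 of at least 1.5, so an item sum of at least 10.5, which means 11 in whole scores. Removing one item of at most 6 leaves A ≥ 5. A = 0 therefore needs a post-baseline reference visit at which the other six items are all 0. When item 7 is one of the six, as it is for any item that may be imputed, FEV1 must be above 95% predicted. Post-baseline references are the first choice, so the case can arise.

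**4. Dependence on the data cut.** ACQ-7 is scheduled on Days 30, 86, 183 and 364. For a missing Week 26 item the first reference is Week 52 and the second is Week 12. At the interim freeze some patients have Week 52 data and others do not (SAP 2.9.2). A score imputed from Week 12 at the freeze could be imputed from Week 52 later. Protocol sections 3.5 and 9 repeat the primary and secondary objectives of CSR I in CSR II.

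**5. Direction.** Take all items 3 at Week 26 and all 1 at Week 52. Then A = 6, B = 18, and the imputed item is 18/6 × 1 = 3, which is exact. The B/A factor scales for improvement after Week 26. The item comes out too high only if it improves proportionally less than the other six, and too low if it improves more.

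**6. Effect on group means.** Assume 1% to 5% of patients have a missing item, all in one group, each shifted by 0.125. The shift is 0.01 × 0.125 = 0.001 to 0.05 × 0.125 = 0.006. One patient like the one in step 2, in a pooled group of 2 × 400 × 0.9 = 720, adds 0.57/720 = 0.0008.

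**7. AQLQ.** Items run from 1 to 7, so A cannot be 0, but imputed values above 7 are possible.

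**The case against.** The strongest reply is that interpolation is plainly intended. The sentence on one missing response is the more specific one, it says the item will be imputed, and the example divides by 7. The mean-of-answered sentence can then be read as only the condition for scoring at all. That largely stands: the conflict is a drafting fault, and one edited clause settles it. But nothing in the text makes the first sentence subordinate, and it does state a formula.

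It is also fair that the A = 0 case is narrow. The case in step 2 needs six items averaging 1 at a visit where the missing item scored 3. SAP 2.9.2 says the key secondary objective is analysed only for the Primary Analysis CSR, so a later change would be a reporting discrepancy and not a second confirmatory test. All of that stands. It does not remove the missing limit or the missing fallback.

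Two stronger readings are tempting and are not supported. A reader might infer that using the later visit first inflates Week 26 scores in patients who improve; step 5 shows that it does not do so systematically. A reader might also set a one-patient shift of 0.95 against the planned 0.15. That compares an individual score with a difference in group means. Replacing interpolation by mean-of-answered, or taking the previous visit first, is a preference. The SAP does use mean-of-answered for ACQ-5 (2.6.2.3), but that does not make it the required rule for ACQ-7.

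**Conclusion.** The rule is wrong as written, and the fault is minor. Followed literally, it can give a patient two scores (3.38 or 3.50 in the SAP's example), an item outside 0-6, or no defined score. A Week 26 value may also change between the two reports. A single score can move by more than the 0.5 used to define ACQ response, so an individual classification could change.

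The key secondary conclusion is unlikely to change. The estimate of 0.001 to 0.006 rests on an assumed 1% to 5% of affected patients, all in one group, each shifted by the 0.125 of the SAP's example. The true rate is not in the documents. Rare extreme ratios would weigh more: the formula's ceiling is 36/1 × 6 = 216 for one item. That is a reason for a limit and not a forecast. No directional bias in the treatment comparison is shown.

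**What to change.** In SAP 2.6.1.1.2:

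1. Keep interpolation as the single rule when one of items 2 to 6 is missing, and keep the first sentence only as the condition for scoring.
2. Limit an imputed item to 0-6. State the matching limit of 1-7 for AQLQ in 2.6.2.8.
3. Name mean-of-answered as the fallback when A = 0 or when no usable reference visit exists.
4. State that Week 26 scores stay as derived at the primary analysis and are not re-imputed when Week 52 data arrive.

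The cost is a few lines of SAP text and derivation code. It needs no new data and no change to the model, sample size or testing procedure. It should be settled before the unblinding for the primary analysis.

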2.6.1.2 Statistical model, hypothesis, and method of analysis

Primary variable

The primary objective to demonstrate superiority of either QMF149 150/160 µg to MF 400 µg or QMF149 150/320 µg to MF 800 µg in terms of trough FEV₁ after 26 weeks of treatment will be evaluated by testing the following null hypotheses (H₀) versus the alternative hypotheses (H_a):

H₀₁: QMF149 150/160 µg is equal to MF 400 µg

versus

H_{a1}: QMF149 150/160 µg is not equal to MF 400 µg

and

H₀₂: QMF149 150/320 µg is equal to MF 800 µg

versus

H_{a2}: QMF149 150/320 µg is not equal to MF 800 µg

The primary variable, trough FEV₁ at Week 26, will be analyzed using a mixed model for repeated measures (MMRM) on the FAS. The model will contain treatment, age group (12 to 17, or ≥ 18 years), region (Eastern Europe, Western Europe, India, Japan, other Asia, rest of world), visit (Days 2, 184, and 365), and treatment-by-visit interaction as fixed effects with baseline FEV₁ measurement, baseline-by-visit interaction, FEV₁ prior to inhalation and FEV₁ within 15 to 30 min post inhalation of salbutamol/albuterol (components of short acting beta-2 agonist (SABA) reversibility) as covariates, and center nested within region as a random effect. The within-patient correlation will be modeled using an unstructured covariance matrix in the mixed model. The Kenward-Roger approximation will be used to estimate denominator degrees of freedom (Kenward and Roger, 1997).

For the primary analysis, if the model does not converge, data only up to week 26 (i.e., Days 2 and 184) will be used (with unstructured covariance matrix). If still the model fails to converge, compound symmetry covariance matrix will be used. If model still does not converge, the random effects of center will be removed. For the final analysis, if the model does not converge with unstructured covariance matrix, the compound symmetry covariance matrix will be used in the mixed model. If still the model does not converge, the random effects of center will be removed. For both analyses, if the model converges after removing the random center effects, the original model without random center effects will be re-assessed. If the final model for the primary analysis converges without Week 52 data, only summary statistics will be provided for Week 52 data analysis. Restricted maximum likelihood method will be used.

The MMRM is based on the missing at random (MAR) assumption where missingness is independent of the unobserved data provided that relevant observed data are accounted for in the statistical model.

Baseline FEV₁ is defined as the mean of the 45 min and 15 min pre-evening dose FEV₁ measurements at Day 1 (V201). If one of the two measurements is missing, the non-missing measurement will be taken as the baseline FEV₁. If both are missing, the pre-bronchodilator reversibility measurement (at V101 or repeated V101) will be used as baseline FEV₁.

Each between-treatment comparison will be carried out using the adjusted mean (least-squares mean) difference based on the treatment main effect and the coefficient for the treatment-by-visit interaction factor corresponding to Day 184. The estimated adjusted treatment difference (QMF149 – MF) will be displayed along with the associated standard error (SE), 2-sided 95% confidence interval (CI), and p-value (2-sided).

Key secondary variable

The key secondary objective to demonstrate superiority of QMF149 (150/160 µg and 150/320 µg combined) to MF (400 and 800 µg combined) in terms of ACQ-7 after 26 weeks of treatment will be evaluated by testing the following null hypothesis (H₀) versus the alternative hypothesis (H_a):

H₀₃: QMF149 (150/160 & 150/320 µg combined) is equal to MF (400 & 800 µg combined)

versus

H_{a3}: QMF149 (150/160 & 150/320 µg combined) is not equal to MF (400 & 800 µg combined)

ACQ-7 after 26 weeks of treatment will be analyzed using the same MMRM (including all scheduled visits with ACQ-7 data) on the FAS as used for the primary analysis but will include baseline ACQ-7 score instead of baseline FEV₁.

To demonstrate the add-on effect of indacaterol over MF for combined doses, the average of following treatment contrasts will be computed:

QMF149 (150/160 µg) vs. MF 400 µg

QMF149 (150/320 µg) vs. MF 800 µg

Least squares means (95% CI) will be presented graphically to assess the interaction between QAB and dose levels of MF.

The doses-combined between-treatment comparison as well as each individual between-treatment comparison will be carried out using the adjusted mean (least-squares mean) difference based on the treatment main effect and the coefficient for the treatment-by-visit interaction factor corresponding to Day 184. The estimated adjusted treatment difference (QMF149 – MF) will be displayed along with the associated standard error (SE), 2-sided 95% confidence interval (CI), and p-value (2-sided).

2.6.1.3 Multiplicity adjustment

To control the family-wise type-I error rate at the two-sided 5% significance level, a multiple testing procedure based on the trimmed Simes test as described in Brannath et al (2009) will be used. The family for the overall type-I error rate control contains three hypotheses: two hypotheses for the primary endpoint trough FEV₁ and one hypothesis for the key secondary endpoint ACQ-7. Denote the two hypotheses for the primary endpoint as H1 and H2 for comparing QMF149 150/160 µg vs. MF 400 µg and QMF149 150/320 µg vs. MF 800 µg respectively. Similarly, denote the hypothesis as H3 for the key secondary endpoint ACQ-7, for comparing QMF149 vs. MF combined doses.

Below is a brief description of the testing procedure based on the trimmed Simes test in Brannath et al (2009).

Let p₁, p₂, p₃ be the corresponding p-values (2-sided) of the three hypotheses of H1, H2, and H3.

Step 1: Retain both H1 and H2 if p_i ≤ 0.05 **AND** the observed treatment difference for the corresponding p_i is in the wrong direction (i.e. MF is performing better than QMF) for **ANY** i = 1, 2, stop here; otherwise go to Step 2.

Step 2: Reject H1 and H2 if p_i < 0.05 for **BOTH** i=1, 2 and go to Step 3; otherwise go to Step 4.

Step 3: Reject H3 if p₃ < 0.05 and stop;

Step 4: If neither Step 1 nor 2 applies, perform the Bonferroni test to H1 and H2. Thus reject H1 if p₁ < 0.025 or reject H2 if p₂ < 0.025 and stop.

For each of the three hypotheses, the corresponding testing statistics (estimated least square mean difference) follows normal distribution. Hence for H1 and H2, their corresponding testing statistics follow jointly bivariate normal distribution. Therefore this testing procedure controls the overall type I error rate at the 2-sided 0.05 level in the strong sense regardless if the bivariate normal distributions have positive or negative correlations as shown in Brannath et al (2009).

Other than the 3 treatment comparisons mentioned above for the primary and the key secondary endpoint, all other analyses will be performed at the nominal 2-sided 0.05 level (2-sided) without multiplicity adjustment.

2.6.1.4 Supportive analyses for the primary objective

As supportive analysis, the same MMRM used in the primary analysis will be also performed on the PPS to assess the treatment effect in protocol adherers.

In addition, the same primary MMRM on the FAS will be performed including all spirometric measures irrespective of single depot corticosteroid injection, other systemic corticosteroid use, or rescue medication use. However, measures taken outside of the 22 – 25 hour post-evening dose window for o.d. regimens (or 8 - 13 hour post-morning dose window for b.i.d. regimens) will be excluded.

As a further sensitivity analysis, a so-called 'tipping point analysis' will be performed for the primary endpoint to evaluate the impact of a deviation from the MAR assumption. The delta-adjusting approach described in Ratitch et al (2013) will be used to find the tipping point, in a spectrum of conservative missing not at random (MNAR) assumptions, at which conclusions change from being favorable to QMF149 to being unfavorable. After such a tipping point is determined, clinical judgment can be applied as to the plausibility of the assumptions underlying this tipping point. This methodology would provide a good picture of what it would take to overturn study conclusions on the basis of varying assumptions about missing data. The basic idea is to first impute the missing Week 26 values using the multiple imputation (MI) method based on the missing at random (MAR) assumption. The imputed Week 26 values for the QMF149 arms are then adjusted by a delta value. A detailed description of the analysis steps is provided in [Appendix 16.1.9](#).

The following ██████████ subgroup analyses for trough FEV₁ using MMRM will be performed (using the appropriate interaction term in the model and additional covariate as a fixed effect if necessary) for the FAS to explore the treatment effect in:

- Age group (12 to 17 years, ≥ 18 years)
- Race (Caucasian, Asian, Black and other)
- Sex (male, female)
- History of asthma exacerbation in the 12 months prior to screening (Yes, No)
- Patients' prior therapies before run-in period (medium dose of ICS, high dose of ICS, and low dose ICS/LABA; see Appendix 11 of the study protocol for the definition of ICS dose levels)
- Pre-bronchodilator FEV₁ in % of predicted FEV₁ at run-in visit 101 (50% to < 60%, 60% to < 85%)
- ACQ-7 at baseline (1.5 - < 2, 2 - < 2.5, ≥ 2.5)

2.6.2 Analysis of secondary variables

Three treatment comparisons will be performed on all secondary variables: 1) QMF149 150/160 µg vs. MF 400 µg, 2) QMF149 150/320 vs MF 800 µg, 3) QMF149 150/320 µg vs. salmeterol xinafoate /fluticasone propionate 50/500 µg b.i.d.. The third comparison will be done on the key secondary variable too and on the primary variable as described below.

2.6.2.1 Comparison of QMF149 150/320 µg vs salmeterol xinafoate/fluticasone propionate 50/500 µg b.i.d. in term of trough FEV₁ at Week 26

QMF149 150/320 µg will be compared to active control (salmeterol xinafoate /fluticasone propionate 50/500 µg b.i.d.) for non-inferiority and – if non-inferiority is shown – for superiority on the primary endpoint. The same MMRM as specified above will be applied. The margin for non-inferiority is defined as 90 mL (see Appendix 12 of the study protocol for the estimation of non-inferiority margin). The result will be interpreted based on the two-sided 95% confidence interval (CI) of the treatment difference QMF149 – active control. The lower bound of the 95% CI is the difference that can be ruled out, i.e., if the lower bound of the 95% CI is larger than the non-inferiority margin of -90 mL, then QMF149 150/320 µg can be considered non-inferior to active control, and if the lower bound of the 95% CI is greater than 0, then QMF149 150/320 µg can be considered superior to active control with regard to trough FEV₁ at Week 26. Note that the comparison versus active control is not part of the confirmatory testing strategy.

2.6.2.2 Spirometry data other than the primary endpoint

Trough FEV₁ at Day 2 and at Day 365 will be analyzed using the same MMRM as specified for the primary analysis and between-treatment comparison will be carried out using the adjusted mean (least-squares mean) difference based on the treatment main effect and the coefficient for the treatment-by-visit interaction corresponding to the respective visit. Adjusted mean (LS mean) will be displayed for each treatment group (for both the absolute FEV₁ value and the change from baseline value) along with the estimated treatment differences and the 95% confidence intervals and the two-sided p-values by visit.

In addition to trough FEV₁, pre-dose trough FEV₁ is defined as the average of the two FEV₁ measurements taken 45 min and 15 min pre-evening dose. Measurements will be done at Days 30, 86, 183, and 364. As for all spirometry data, measurements taken within 6 hours of rescue medication use or within 7 days of systemic corticosteroid use or within 3 months of a single depot corticosteroid injection will be set to missing. However, the post-evening dose time window of 22 – 25 hours or the post-morning dose time window of 8 – 13 hours cannot be applied here since the dosing data of the previous day or the morning of the day of pre-dose measurements will not be recorded. The same MMRM as for trough FEV₁ will be applied, however, with other visits included.

Post-dose FEV₁ measurements (5 min, 15 min, 30 min, 1 hr) will be analyzed separately by visit using the same MMRM as for trough FEV₁ with post-dose time point as repeat variable (i.e., in the MMRM, visit will be replaced by time point).

Pre- and post-dose FVC and FEF₂₅₋₇₅ will be analyzed similar to FEV₁.

To estimate the add-on effect of indacaterol to existing MF treatment (in terms of trough FEV₁), the average difference between QMF149 and MF will be computed across two dose levels. This difference is interpreted as an average effect of adding indacaterol to MF, under the assumption that indacaterol effect is not altered by dose of MF. To compute the difference, the QMF149 and MF doses will be pooled by averaging the following contrasts within the MMRM model, as specified for the primary analysis:

- QMF149 (150/160 µg) vs. MF 400 µg
- QMF149 (150/320 µg) vs. MF 800 µg.

For all spirometry measurements, we exclude the implausible values. Specifically, if a patient has implausible FEV₁ value (defined as > 7 L) at an assessment, all spirometry measurements related to that assessment will be excluded. The threshold of 7 L was chosen because according to ERS/ECCS 1993 regressions, the maximum normal predicted FEV₁ is 5.17 L, we set 7 L as the implausible cutoff to allow for some fluctuation around the maximum mean.

2.6.2.3 ACQ at Weeks 4, 12 and 52

ACQ-7 at Weeks 4, 12 and 52 will be analyzed using the same MMRM as specified for the key secondary endpoint ACQ-7 at Week 26. Change from baseline in the ACQ-7 will be also analyzed using the same MMRM model.

In addition, the proportion of patients who achieve an improvement of at least 0.5 in ACQ-7 (i.e., a decrease of ACQ-7 score of at least 0.5 from baseline) at Week 4, 12, 26, and 52 visits will be analyzed using a logistic regression model. First, missing continuous ACQ-7 values will be imputed using a MI method under MAR assumption. Then continuous ACQ values will be converted into binomial responses and generalized estimating equation (GEE) method will be used to analyze the imputed datasets and then the results from GEE method will be combined for the inference. The model will include the same terms as used for the analysis of ACQ-7 but no random effect for center nested within region. The estimated adjusted odds ratios will be displayed along with the associated 95% (two-sided) confidence intervals and p-values.

In addition to the contrast of QMF149 average vs. MF average, the individual treatment contrasts of QMF149 (150/160 µg) vs. MF 400 µg and QMF149 (150/320 µg) vs. MF 800 µg will be presented.

Additionally, the number (%) of patients will be summarized by visit with the following categories: Response (decrease from baseline of ≥ 0.5 units in ACQ-7), no change ($-0.5 <$ change from baseline in ACQ-7 < 0.5), worsening (increase from baseline of ≥ 0.5 units in ACQ-7). Net response is expressed as the number of patients with response – the number of patients with worsening.

All the analyses described above will be repeated for ACQ-5, including the responder analysis with the same threshold of 0.5..

The ACQ-5 consists of five items on symptom assessment, which is a subset of ACQ-7. All 5 questions of the ACQ-5 are equally weighted. The total score is calculated as the mean of all five questions, which is calculated as the sum of scores divided by the number of questions that were answered, as long as there were at least 4 questions answered and the missing question is

not Question 1 ('On the average, during the past week, how often were you woken by your asthma during the night?').

